6.2 Dose adjustment guidelines for non-hematologic ibrutinib or selinexor-related toxicities

Specific guidelines are provided below for non-hematologic toxicities. For all other grade 3 non-hematologic toxicities possibly related to study therapy, hold the causative agent, or if the causative agent cannot be determined, hold both ibrutinib and selinexor. Once the toxicity is improved to ≤ Grade 2 or until baseline pre-treatment value, resume treatment with a decrease in the dose of ibrutinib by 140 mg or selinexor by one dose level. No dose reduction below ibrutinib 140 mg and selinexor 20 mg/week will be allowed. If a patient experiences several adverse events, and there are conflicting recommendations, the investigator should use the

recommended dose adjustment that reduces the dose to the lowest level. Missed doses will not be replaced. Treatment delays for adverse events exceeding 28 days will lead to protocol removal.

Any Grade 4 toxicities (lasting ≥ 7 days for transaminase or electrolyte abnormalities) that are at least possibly attributed to selinexor or ibrutinib should result in permanent discontinuation of the causative agent. If attribution to a single drug cannot be made, both drugs should be discontinued.

Event Name	Nausea	
Grade of Event	Management/Next Dose Ibrutinib	Management/Next Dose of Selinexor
Grade 1	No change in dose	5-HT3-antagonists, D2-antagonists or NK1 antagonists, or dronabinol or combinations can prevent nausea in the majority of patients. Consider additional anti-emetics (see the NCCN Clinical Practice Guideline for antiemesis). Provide guidance on diet as described above for anorexia as increased caloric intake may reduce nausea.
Grade 2	No change in dose	Implement one or more combinations of anti-nausea medications. Consider additional anti-emetics (see the NCCN Clinical Practice Guideline for antiemesis). If Grade 2 nausea persists, reduce dose of selinexor by one dose level. If patient's nausea is Grade ≤ 1 for 4 weeks, then the dose of selinexor may be increased back to the previous dose level.
Grade 3	No change in dose	Interrupt dosing of selinexor and implement one or more combinations of anti-nausea medications. Consider additional anti-emetics (see the NCCN Clinical Practice Guideline for antiemesis). Ensure adequate caloric and fluid intake. Restart selinexor with one dose level reduction when nausea is Grade ≤ 2 and adequate caloric and fluid intake have been achieved. If patient's nausea is Grade ≤ 1 for 4 weeks, then the dose of selinexor may be increased back to the previous dose level.

Recommendations:
 
-Full supportive care and antiemetics. See Section 4.4.
 
- If the patient tolerates a reduced dose for two cycles, patient may be dose escalated to the dose they received prior to the reduction after authorization from Principal Investigator.
		
---	--	--

Event Name	Vomiting	
Grade of Event	Management/Next Dose Ibrutinib	Management/Next Dose of Selinexor
≤ Grade 2	No change in dose	No change in dose
Grade 3	No change in dose	Hold until toxicity ≤ Grade 1. Decrease by one dose level.

Recommendations:
 
-Full supportive care and antiemetics. See Section 4.4.
		

Event Name	Diarrhea	
Grade of Event	Management/Next Dose Ibrutinib	Management/Next Dose of Selinexor
Grade 1	No change in dose	Rule out other causes of diarrhea, including infectious agents. At the first sign of abdominal cramping, loose stools, or onset of diarrhea, it is recommended that the patient be treated according to institutional standard of care, e.g., loperamide (Immodium®). Maintain dose level of selinexor.
Grade 2	No change in dose	If diarrhea is present despite maximal anti-diarrheal medication, rule out other causes of diarrhea, including infectious agents. Reduce selinexor by one dose level until resolved to ≤ Grade 1, then re-start at the current dose level. If diarrhea returns as Grade ≥ 2, then reduce selinexor dose by one dose level. If patient is stable and diarrhea resolves (Grade 0 or baseline with or without anti-diarrheals) for 4 weeks, then the patient's dose may be re-escalated
Grade 3	Hold until ≤ Grade 1. Decrease ibrutinib to next lowest dose level.	If diarrhea is present despite maximal anti-diarrheal medication, rule out other causes of diarrhea, including infectious agents. Delay selinexor until

		resolved to Grade ≤ 2 , then reinitiate selinexor at one dose level below. If patient is stable and diarrhea resolves (Grade 0 or baseline with or without anti-diarrheals) for 4 weeks, then the patient's dose may be re-escalated.

Recommendations:
 
-Full supportive care and antidiarrheal agents. See Section 4.4.
		

Event Name	Fatigue	
Grade of Event	Management/Next Dose Ibrutinib	Management/Next Dose of Selinexor
Grade 1	No change in dose	Ensure adequate caloric intake and assess volume status. Recommend high calorie and/or energy drinks and/or foods. Adjust other medications. Rule out other causes of fatigue such as adrenal insufficiency, hypothyroidism, etc.
Grade 2	No change in dose	Ensure adequate caloric and fluid intake and assess volume status. Add supportive care for fatigue, or reduce the dose of selinexor by one level. If patient's fatigue is Grade ≤ 1 for 4 weeks, then the dose of selinexor may be increased back to the previous dose level.
Grade 3	No change in dose	Ensure adequate caloric and fluid intake and assess volume status. Interrupt selinexor dosing until resolved to Grade ≤ 2 , reduce dose of selinexor by 1 level. If patient's fatigue is Grade ≤ 1 for 4 weeks, then the dose of selinexor may be increased back to the previous dose level.

Recommendations:
 
- Optimize supportive care including caloric and fluid intake. Add glucocorticoids when not contra-indicated. See Section 4.4.
		

Event Name	Rash - Maculopapular	
Grade of Event	Management/Next Dose Ibrutinib*	Management/Next Dose of Selinexor*
\leq Grade 1	No change in dose	No change in dose
Grade 2	Hold until \leq Grade 1. Resume same dose.	No change in dose

Grade 3	Hold until toxicity \leq Grade 1. • 1 st occurrence: Decrease ibrutinib to next lowest dose level. • 2 nd occurrence: Decrease ibrutinib to next lowest dose level.	Hold until toxicity \leq Grade 1 or baseline. • 1 st occurrence: No change in dose. • 2 nd occurrence: Decrease selinexor to next lowest dose level.
*Dose reductions < ibrutinib 140 mg daily or selinexor 20 mg weekly are not permitted. Recommendations: - Review medication list and discontinue any medications that commonly cause rash if possible. -Consider skin biopsy.		

Event Name	Thrombosis/Thromboembolic Event	
Grade of Event	Management/Next Dose Ibrutinib	Management/Next Dose of Selinexor
\leq Grade 1	No change in dose	No change in dose
Grade 2 or 3	Hold until therapeutically anticoagulated and platelets are \geq 50,000/mm ³ . Resume at the same dose level.	Hold until therapeutically anticoagulated and platelets are \geq 50,000/mm ³ . Resume at the same dose level.
Recommendation: Anticoagulation (warfarin prohibited)		

Event Name	Hyponatremia	
Grade of Event	Management/Next Dose Ibrutinib	Management/Next Dose of Selinexor
Grade 1 (Lower Limit of Normal to 130 nM)	No change in dose	Maintain selinexor dose and frequency level, assure adequate fluid, electrolyte and caloric intake, adjust other medications, and consider salt supplementation 1-3 times per day. Correct sodium level for hyperglycemia (serum glucose >150 mg/dL). Rule out other causes of low sodium (e.g., SIADH, cardiac, hepatic, adrenal, renal, and thyroid diseases, Fanconi Syndrome, diuretic use, etc.).
Grade 3 (126-129 mmol/L)	No change in dose	Ensure patient is euvolemic and has sufficient fluid and electrolyte intake. Replace fluids orally or IV if patient is dehydrated. Correct sodium level for hyperglycemia. Rule out other causes of low sodium (see above for Grade 1). Hold selinexor until hyponatremia

		resolves to Grade ≤ 1 (≥ 130 nM) and initiate aggressive salt supplementation 2-3 times per day. Restart at the same dose and frequency of selinexor and monitor serum sodium closely. If this recurs, measure urine sodium and creatinine levels to investigate for other causes of hyponatremia.
Grade 3 (120-125 mmol/L)	No change in dose	Hold selinexor dose until sodium ≥ 125 mmol/L*. Decrease selinexor to the next lowest dose level for initial and each subsequent occurrence.

*If sodium does not recover to ≥ 125 mmol/L within 14 days of holding selinexor, selinexor should be permanently discontinued
 
 In marked hyperglycemia, ECF osmolality rises and exceeds that of ICF, since glucose penetrates cell membranes slowly in the absence of insulin, resulting in movement of water out of cells into the ECF. Serum Na concentration falls in proportion to the dilution of the ECF, declining 1.6 mEq/ L for every 100 mg/dL (5.55 mmol/L) increment in the plasma glucose level above normal. This condition has been called translational hyponatremia because no net change in total body water (TBW) has occurred. No specific therapy is indicated, because Na concentration will return to normal once the plasma glucose concentration is lowered. Corrected Sodium = Measured sodium + 0.024 * (Serum glucose - 100). 		

Event Name	Anorexia	
Grade of Event	Management/Next Dose Selinexor	
Grade 1		Assess dietary options (e.g., try a variety of other foods). Add high-calorie supplements (e.g., Ensure®). Consider an appetite stimulant(s) (see the NCCN Clinical Practice Guideline for anorexia).
Grade 2		Add high-calorie supplements (e.g., Ensure®). Add an appetite stimulant(s) (see the NCCN Clinical Practice Guideline for anorexia). Selinexor dosing may be interrupted intermittently while supportive medications are instituted, usually for <1 week. If Grade 2 anorexia does not resolve after institution of supportive medications, reduce selinexor dose by 1 level . If patient's anorexia is Grade

		≤1 for 4 weeks, then the dose of selinexor may be increased back to the previous dose level.
Grade 3		Interrupt dosing with selinexor until resolution to Grade ≤2. Add high calorie supplements. As described above, initiate supportive medications for anorexia. Restart selinexor at 1 dose level reduction . once anorexia resolves to Grade ≤ 2 and follow the guidelines above. If patient's anorexia is Grade ≤1 for 4 weeks, then the dose of selinexor may be increased back to the previous dose level.

Event Name	Weight Loss	
Grade of Event		Management/Next Dose of Selinexor
Grade 1		Assess dietary options (e.g. try a variety of other foods). Add high-calorie supplements (e.g., Ensure®). If fatigue or nausea also present, consider corticosteroids on day of and day after selinexor dosing. Consider an appetite stimulant(s) (see the NCCN Clinical Practice Guideline for anorexia and anti-emesis).
Grade 2		Add high-calorie supplements (e.g., Ensure®). Consider corticosteroids on day of and day after selinexor dosing. Consider an appetite stimulant(s) (see the NCCN Clinical Practice Guideline for anorexia and anti-emesis). Consider megestrol acetate 80-400mg daily. Consider anabolic steroids such as oxandrolone. Consider dronabinol (Marinol®). If Grade 2 weight loss does not resolve after institution of supportive medications, reduce selinexor dose by 1 level.
Grade 3		Interrupt dosing with selinexor. Add high calorie supplements. Use supportive medications from above alone or in combinations. Restart

		selinexor at 1 dose level reduction once weight loss resolves to Grade ≤ 2 . If Grade 2 weight loss persists with supportive medications, reduce dose of selinexor by 2 levels. If patient's weight loss is Grade ≤ 1 for 4 weeks, then the dose of selinexor may be increased back to the previous dose level.
--	--	--

Event Name	Hypertension	
Grade of Event	Management/Next Dose Ibrutinib	Management/Next Dose of Selinexor
Grade 1	No change in dose	No change in dose
Grade 2	No change in dose	No change in dose
Grade 3	No change in dose if hypertension is medically managed.	No change in dose
Grade 4	If possibly, probably, or definitely related to ibrutinib, consider holding dose until hypertension improves to baseline with medical management of hypertension. Ibrutinib can then be reinsituted at the same dose at first occurrence. At second occurrence, reduce dose to 280 mg daily.	No change in dose

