5.16 Warfarin

Patients who must receive systemic anticoagulation with warfarin will be excluded secondary to severe bleeding when ibrutinib and warfarin have been used concurrently. Patients must be off warfarin for 30 days prior to enrollment. If individuals develop a DVT or other complications requiring anticoagulation, low molecular weight heparin or thrombin inhibitors may be used. Ibrutinib should be held for a minimum of 7 days to assure acceptable tolerance of this treatment. For patients with low risk atrial fibrillation, aspirin (325 mg/day) is recommended unless the patient is at high risk for thromboembolic complications.

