≥ Grade 3	
Hold until neutrophils, hemoglobin, or platelets have returned to within 50% of pretreatment values. If initial value is within 50% of pretreatment value, no hold is needed.
 
 • 1st occurrence: No change in dose • 2nd occurrence: Cohort 1 and 3= No change in dose; Cohort 2 = Decrease ibrutinib to the next lowest dose level. • 3rd occurrence: Decrease ibrutinib to the next lowest dose level. • 4th occurrence: Patient comes off study 	
Hold until neutrophils, hemoglobin, or platelets have returned to within 50% of pretreatment values. If initial value is within 50% of pretreatment value, no hold is needed.
 
 • 1st occurrence: No change in dose. Initiate granulocyte colony-stimulating factors for grade >3 neutropenia. • 2nd occurrence: Decrease selinexor to next lowest dose. • 3rd occurrence: No change in dose • 4th occurrence: Decrease selinexor to the next lowest dose • 5th occurrence: No change in dose • 6th occurrence: Discontinue selinexor

*Dose reductions < ibrutinib 140mg daily or selinexor 20 mg weekly are not permitted.
 
Recommendations:
 
 -Full supportive care, growth factors, and transfusions should be given as medically indicated. - If the patient tolerates a reduced dose for two cycles, patient may be dose escalated to the dose they received prior to the reduction after authorization from Principal Investigator. 		

Event Name	Bleeding	
Grade of Event	Management/Next Dose Ibrutinib*	Management/Next Dose of Selinexor*
≤ Grade 2 (mild to moderate)	
Hold ibrutinib for at least 7 days after last bleeding and until platelets return to ≥ 50% of baseline value.
 
 • 1st occurrence: Restart ibrutinib at next lowest dose level. In cases where no bleeding is observed after 6 days of dosing return to full dose at the physician's discretion. • 2nd occurrence: Restart ibrutinib at next lowest dose level. • 3rd occurrence: Patient comes off study. 	
Hold selinexor for at least 7 days after last bleeding and until platelets return to ≥ 50% of baseline value.
 
 • 1st occurrence: Restart selinexor at next lowest dose level. In cases where no bleeding is observed after 6 days of dosing return to full dose at the physician's discretion. • 2nd occurrence: Restart selinexor at next lowest dose level. • 3rd occurrence: Patient comes off study.

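### Section 6.2 gives two incompatible rules for Grade 4 hypertension at least possibly related to ibrutinib: permanent discontinuation, or a hold with restart at the same dose

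*Combined protocol and SAP*

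**What the plan says.** **Grade 4 hypertension.** The general text of Section 6.2 says that any Grade 4 toxicity linked at least possibly to a study drug "should result in permanent discontinuation of the causative agent". Its only qualifier is a duration of 7 days or more for transaminase and electrolyte abnormalities. The Grade 4 row of the hypertension table, further down in Section 6.2, reads for ibrutinib: "If possibly, probably, or definitely related to ibrutinib, consider holding dose until hypertension improves to baseline". It goes on: "Ibrutinib can then be reinsituted at the same dose at first occurrence". Then: "At second occurrence, reduce dose to 280 mg daily".

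**Clot.** Section 5.16, for a DVT or another complication that needs anticoagulation, says: "Ibrutinib should be held for a minimum of 7 days to assure acceptable tolerance of this treatment". The thrombosis table in Section 6.2, for Grade 2 or 3, says: "Hold until therapeutically anticoagulated and platelets are" at least 50,000/mm³, followed by resumption at the same dose level. It gives no minimum duration and does not refer to Section 5.16.

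**Repeated cytopenia.** Section 6.1 has one table for normal baseline counts and one for low baseline counts. In the low-baseline table the ibrutinib column takes the patient off study at the 4th occurrence. The selinexor column lowers selinexor at the 4th, leaves the dose unchanged at the 5th, and for the 6th ends "occurrence: Discontinue selinexor".

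**The concern.** For a related Grade 4 hypertension event, a site that restarts ibrutinib under the table breaks the general sentence, and a site that stops it permanently sets aside the table. The event is foreseeable: exclusion criterion 3.2.15 lets patients into Cohort 3 with ongoing Grade 3 or higher hypertension due to ibrutinib, provided it is medically managed.

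Patient safety comes first, because the rule governs re-exposure after a Grade 4 event. The data come second. Safety and tolerability of the combination is a secondary objective (1.2.1). Section 13.8.1 names cycles started and completed, dose reductions and reasons for going off treatment as the measures of tolerability. If sites follow different lines for the same event, those counts partly reflect which line was read.

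The three lesser mismatches raise the same problem in weaker form: a fixed dose step, a hold time that differs between two sections, and two columns of one table that end at different points.

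**Working it through.** The plan gives no figure to reproduce, so the check sets side by side every rule that applies to the same event.

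**1. Grade 4 hypertension**
- Trigger: the general sentence covers Grade 4, at least possibly attributed. The table row covers Grade 4, related possibly or more strongly. The triggers coincide.
- Action after a first event: permanent discontinuation (0% of the prior ibrutinib dose) against an optional hold and restart at the same dose (100%).
- Exemption: the phrase that sets aside toxicities with their own tables belongs to the Grade 3 sentence of Section 6.2. The Grade 4 sentence is unrestricted apart from the duration qualifier, and hypertension is neither a transaminase nor an electrolyte abnormality.
- Other tables: every other table in Section 6.2 stops at Grade 3, which fits a general Grade 4 rule. Hypertension alone has a Grade 4 row.
- Tie-breaker: the lowest-dose rule in Sections 6 and 6.2 is worded for a patient with several adverse events. It does not address two rules for one event.
- Timing: under Section 5.3 a Grade 4 non-hematologic toxicity not otherwise listed is a DLT unless clearly unrelated, subject to the documented case review. Section 6 removes a patient with a cycle 1 DLT from protocol. The conflict therefore operates mainly from cycle 2.

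**2. The fixed 280 mg step**
- Inputs: ibrutinib 420 mg at both dose levels (table in 5.2), and a floor of 140 mg. Assumption: the next lowest level is 140 mg down, the step Section 6.2 uses for other Grade 3 toxicities.
- Other rules can lower the dose first. Two Grade 3 rash events (6.2), or two Grade 4 neutropenic fever events (6.1), give 420 − 140 = 280, then 280 − 140 = 140 mg.
- Change produced by a move to 280 mg: from 420, 280 − 420 = −140 mg; from 280, 280 − 280 = 0; from 140, 280 − 140 = +140 mg. Only the first is a reduction.

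**3. Clot**
- Let *d* be the day on which the table's two conditions are met, counted from the start of the hold. The table allows restart at *d*. Section 5.16 allows it no earlier than day 7. Meeting both means waiting until max(7, *d*).
- A site using only the table can restart earlier by max(0, 7 − *d*) days: at most 7, and none if *d* is 7 or more.

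**4. Low-baseline cytopenia**
- 4th occurrence: off study (ibrutinib column) against a selinexor decrease with treatment continuing (selinexor column). The selinexor column runs 6 − 4 = 2 occurrences further.
- In the normal-baseline table both columns end at the 4th, so there is no conflict there.
- Section 6.1 limits modification to one drug when the event is clearly due to that drug. The conflict remains when attribution is joint or unclear.

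**The case against.** The best defence on hypertension is that a specific table overrides general text. Section 6.2 opens by announcing specific guidelines, the table's wording is permissive, and Section 6.7 requires consultation with the principal investigator on every delay, modification and reintroduction. That reading is natural, and it may be what was intended. But the protocol nowhere says that the table is an exception, and consultation does not tell the sites of a multi-center study which written rule governs.

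The defence has more force on the lesser points, where a reader might infer too much:
- *That the protocol orders a doubled dose at 140 mg.* It does not. The instruction is to reduce, and an increase would contradict that word. Where several adverse events are in play, the tie-breaker may also apply. What stands is that the step gives no reduction for a patient already at 280 or 140 mg.
- *That the two clot rules exclude each other.* They do not. Waiting for the later condition satisfies both, and the table sets no maximum hold. What stands is that neither place says to read them together, so only restart timing differs.
- *That ibrutinib rules contradict each other on a fourth cytopenia.* Both ibrutinib columns agree. The clash is between drug columns, in one of two tables, and disappears when one drug is clearly responsible.

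It is also fair to say that Section 13.8.1 makes the dose-reduction and off-treatment summaries optional.

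**Conclusion.** The concern holds for Grade 4 hypertension at least possibly related to ibrutinib. The two rules cannot both be followed after a first event, and the difference is 0% against 100% of the previous dose. It applies mainly from cycle 2. A reader might infer that the dose-finding result is compromised. The documents do not support that: the primary endpoint is cycle 1 DLT, and a cycle 1 event that counts as a DLT leads to removal under either rule.

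The remaining three are requests for clarification: a fixed step that is not a reduction from 280 or 140 mg; a restart up to 7 days earlier under the thrombosis table alone; and, with joint or unclear attribution, a table that ends at the 4th occurrence for one drug and the 6th for the other.

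The conclusion assumes that the Grade 4 sentence means what it says for non-hematologic events generally. The 280 mg point also assumes a 420 mg start and 140 mg steps. The documents do not allow an estimate of how many patients would be affected.

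**What to change.** By amendment, the sponsor should reconcile:

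1. the general Grade 4 sentence of Section 6.2 with the Grade 4 row of the hypertension table, including how the fixed 280 mg step fits with the reductions elsewhere in Sections 6.1 and 6.2 that can already have brought a patient to 280 or 140 mg;
2. the hold in Section 5.16 with the hold in the thrombosis table of Section 6.2;
3. the ibrutinib and selinexor columns of the low-baseline cytopenia table in Section 6.1, for events whose attribution is joint or unclear.

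The aim is one rule per event. Which rule stands is for the sponsor's clinical team, and this review takes no view on it. The cost is wording in these few places, with no new procedures, assessments or patients.

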Grade 3 with sodium levels <130-120 mmol/L without symptoms	
Rule out other causes including drug (eg, diuretic) effects. Be certain that reported sodium level is corrected for concurrent hyperglycemia (serum glucose >150 mg/dL).
 
If (corrected) sodium is Grade ≤ 3 and continues to be asymptomatic, then patient may continue current dosing without interruption provided that IV saline and/or salt tablets are provided and patient is followed closely.
 
If Grade 3 is persistent or worsens or does not respond to treatment, interrupt selinexor dosing until resolved to Grade 1 or baseline and reduce selinexor by 1 dose level.

Grade 3 with sodium levels <130-120 mmol/L with symptoms or Grade 4 (<120 mmol/L)	
Rule out other causes including drug (eg, diuretic) effects. Be certain that reported sodium level is corrected for concurrent hyperglycemia (serum glucose > 150 mg/dL).
 
Interrupt selinexor dosing until resolved to Grade 1 or baseline and without symptoms. Reduce selinexor by 1 dose level.

Diarrhea	
Grade 1	
Maintain dose. Rule out other causes including drug effects. Treat per institutional guidelines with anti-diarrheals, such as loperamide.

Grade 2	
Rule out other causes including drug effects. Treat per institutional guidelines with anti-diarrheals. Interrupt selinexor dosing until resolved to Grade 1 or baseline.
 
For first occurrence, restart selinexor at current dose.
 
For \geq second occurrence, reduce selinexor by 1 dose level.

Grade 3 or 4	
Interrupt selinexor dosing until resolved to Grade 1 or baseline and patient is clinically stable. Reduce selinexor dose by 1 dose level.

Thrombocytopenia	
Grade 1 or 2	
Maintain dose. Rule out other causes including drug effects.

Toxicity and Intensity	Supportive Care and Dose Adjustment Guidelines

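### After a sodium of 120-125 mmol/L, section 6.2 lets selinexor restart (one dose level lower) at 125; after the milder 126-129 event it requires 130

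*Combined protocol and SAP*

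**What the plan says.** The hyponatremia table in section 6.2 has two Grade 3 rows for selinexor.

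- **126-129 mmol/L.** The instruction is "Hold selinexor until hyponatremia" has resolved to Grade 1 or less, which the row gives as at least 130. (The unit is printed as nM; mmol/L is evidently meant.) Then: "Restart at the same dose and frequency of selinexor and monitor serum sodium closely".
- **120-125 mmol/L.** The instruction is "Hold selinexor dose until sodium" is at least 125 mmol/L. Then: "Decrease selinexor to the next lowest dose level for initial and each subsequent occurrence". A footnote adds that if sodium is not back to at least 125 "within 14 days of holding selinexor, selinexor should be permanently discontinued".

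The supportive-care table in section 5.18 covers the same sodium range. An asymptomatic Grade 3 patient "may continue current dosing without interruption provided that IV saline and/or salt tablets are provided and patient is followed closely". If the event persists, worsens or does not respond, the site must "interrupt selinexor dosing until resolved to Grade 1 or baseline and reduce selinexor by 1 dose level". For symptomatic Grade 3 or for Grade 4 the rule is "Interrupt selinexor dosing until resolved to Grade 1 or baseline and without symptoms", again with a one-level reduction.

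Section 6.5 exempts reversible electrolyte abnormalities from a selinexor hold. Section 6.7 requires consultation with the principal investigator on every reintroduction.

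**The concern.** A recovery threshold should not become easier to meet as the event gets worse. Here a patient who rises from 122 to 127 may be re-dosed, while a patient who falls from 131 to 127 must be held until 130. The table calls 127 Grade 3 in both cases. A sodium of exactly 125 lies in the hold range and already satisfies the restart condition.

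A site that follows the table can therefore re-expose a patient at a lower sodium after the more severe event. It will also meet a different rule in section 5.18 for some of the same patients, and nothing says which section governs.

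**Working it through.** The plan states no figure to reproduce. The check compares the restart rules side by side.

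| Rule | Event | Restart sodium | Restart dose |
|---|---|---|---|
| 6.2 | 126-129, Grade 3 | ≥130 (Grade ≤1) | same |
| 6.2 | 120-125, Grade 3 | ≥125 | one level lower |
| 5.18 | Grade 3, persistent, worsening or unresponsive | Grade 1 or baseline | one level lower |
| 5.18 | Grade 3 with symptoms, or Grade 4 | Grade 1 or baseline, no symptoms | one level lower |

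**Size of the inversion.** 130 − 125 = 5 mmol/L. Under the row as written, restart below 130 is allowed at 125, 126, 127, 128 and 129: five whole-number values, all labelled Grade 3. If a site moved a patient who had risen to 126-129 into the milder row, which the protocol does not instruct, only 125 would remain. Restart would then be allowed at 125 and withheld at 126-129.

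**Is 125 a misprint?** The footnote repeats it as the recovery value, so neither a slip in one cell nor a text-extraction fault is likely.

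**Does it fit the rest of 6.2?** Where 6.2 holds selinexor for another Grade 3 event and names a recovery grade, that grade is below 3: at most 2 for nausea, diarrhea, fatigue, anorexia and weight loss; at most 1 for vomiting; at most 1 or baseline for rash. The default for unlisted Grade 3 events is at most Grade 2 or baseline. Neither sodium table has a Grade 2 row, so a requirement to fall below Grade 3 means 130.

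**Time available if the value becomes 130.** A patient who reaches 125 by hold day 14 has 28 − 14 = 14 days before the 28-day delay limit. Section 6 lets the principal investigator approve an exception to that limit; the repeat of the rule in 6.2 does not mention one.

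**Cycle 1 doses.** Selinexor is given on days 1, 8 and 15 (section 5.2.3), and section 5.3 requires at least 2 of the 3 doses for DLT assessment. Assume held doses are not made up.

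- Event found on day 8 before dosing, sodium 125-129 on day 15. Current row: days 1 and 15, 2 of 3, evaluable. Restart at 130: day 1 only, 1 of 3, not evaluable.
- Event first found on day 15 before dosing: days 1 and 8, 2 of 3 under both rules.

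**The case against.** The strongest defence is that the lower value is a trade-off. The 120-125 row cuts the dose at every occurrence and stops selinexor permanently if sodium is still below 125 after 14 days; the milder row restarts at full dose. From 40 mg weekly the next level is 20 mg weekly, a halving (20/40) and also the dose floor. This softens the inversion but does not explain it. Section 5.18 makes the same one-level cut and still requires Grade 1 or baseline, and the documents give no rationale for 125.

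A second defence is that the principal investigator reviews every reintroduction under 6.7. That is a real safeguard, but it supplies no sodium value. The rule in section 6 for conflicting recommendations does not either: it addresses several adverse events and selects a dose level.

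A third is that the protocol accepts some dosing at Grade 3 sodium. This stands. A reader might infer from the table that any dosing at 125-129 breaches the plan's own safety standard; sections 5.18 and 6.5 do not support that. They allow it for asymptomatic patients who are treated and followed, or for reversible abnormalities. What they leave unexplained is why the restart value is lower after the worse of two events that are both held.

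Finally, the cycle 1 cost may be narrower than the dose count suggests. Under 5.3 a Grade 3 electrolyte abnormality that supportive therapy cannot correct is not excepted from DLT, and section 6 removes patients with a cycle 1 DLT. Some patients stuck at 125-129 would never reach the restart question.

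**Conclusion.** The inconsistency is real and should be corrected as a minor patient-safety and consistency point. It affects patients with a 120-125 mmol/L event whose sodium has recovered only to 125-129. The gap is 5 mmol/L, taking the rows as written and mmol/L as the unit throughout. Their number cannot be stated, because the documents give no hyponatremia rate.

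A reader might infer that restarting at 125 has been shown to be unsafe. The documents compare no outcomes at 125 and 130, so only the ordering of the two thresholds and the conflict with 5.18 are established. A reader might also infer that the DLT definition or the statistical figures are wrong. The inversion leaves both as they are; the link to DLT assessment comes from the longer hold that the correction can cause.

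**What to change.** In the 120-125 mmol/L row of the 6.2 hyponatremia table, change the restart condition to Grade 1 or less (at least 130 mmol/L). Keep the one-level dose reduction. Keep the 14-day discontinuation footnote at 125, so that 125 decides whether selinexor is stopped for good and 130 decides when it restarts. If a baseline alternative is wanted, add it to both Grade 3 rows. Added only to the 120-125 row, it would let a patient with a baseline of 127 restart at 127 after the worse event but wait for 130 after the milder one.

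Leave 6.5 unchanged: its exemption is a separate, stated policy. This edit also does not settle whether asymptomatic Grade 3 patients may continue (5.18) or must be held (6.2).

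The change is one value in one row, with no new tests or patients. Its downside is a longer hold for patients who plateau at 125-129. In cycle 1 that can cost the 2-of-3 dose requirement for DLT assessment, and a hold beyond 28 days could count under the treatment-delay criterion in 5.3.
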